## 7.1 Screening

### Within 28 days of study registration

- Informed consent statement
- Complete medical history
- Complete physical examination
- Vital signs including blood pressure (BP), height, weight and ECOG performance status
- Adverse event and concomitant medication assessment
- Local pathology review for confirmation of adenocarcinoma
- CT scans of the chest, abdomen, and pelvis to assess all measurable or non-measurable sites of disease

### Within 7 days of study registration

- ECOG performance status
- Laboratory testing:
  - Complete Blood Count (CBC) with differential and platelet count
  - Complete metabolic profile (CMP) including: serum chemistries (creatinine, glucose, total protein, blood urea nitrogen [BUN], total carbon dioxide [CO2], albumin, total bilirubin, alkaline phosphatase, and aspartate transaminase [AST] and alanine transaminase [ALT]) and electrolytes (total calcium, chloride, potassium, sodium)
  - PT/INR and aPTT
  - Urine pregnancy test or serum HCG (only for women of child bearing potential)
  - Urinalysis should be done if proteinuria is suspected as per site investigator's discretion.

## 7.2 On Treatment

### 7.2.1 Cycle 1 Day 1

**NOTE:** Cycle 1 Day 1 testing need not be repeated if completed within 7 days of starting protocol therapy.

- Complete physical examination
- Vital signs including BP, weight and ECOG performance status
- Adverse event and concomitant medication assessment
- MFSI-SF and PROMIS questionnaires
- Drug administration as outlined in Section 5 and Study Calendar

### 7.2.2 Cycle 1 Day 15 ( $\pm$ 3 days)

- Complete physical examination
- Vital signs including BP, weight and ECOG performance status
- Laboratory testing:
  - Complete Blood Count (CBC) with differential and platelet count
  - Complete metabolic profile (CMP)
- Adverse event and concomitant medication assessment
- Drug administration as outlined in Section 5 and Study Calendar
- Administer MFSI-SF and PROMIS questionnaires

### **7.2.3 Cycle 2 Day 1 ( $\pm 3$ days)**

- Complete physical examination
- Vital signs including BP, weight and ECOG performance status
- Laboratory testing:
  - Complete Blood Count (CBC) with differential and platelet count
  - Complete metabolic profile (CMP)
  - PT/INR and aPTT
  - Urinalysis should be done if proteinuria is suspected as per site investigator's discretion.
- Adverse event and concomitant medication assessment
- Drug administration as outlined in Section 5 and Study Calendar
- Administer MFSI-SF and PROMIS questionnaires
- Pill Count

### **7.2.4 Cycle 2 Day 15 ( $\pm 3$ days)**

- Complete physical examination
- Vital signs including BP, weight and ECOG performance status
- Complete metabolic profile (CMP)
- Adverse event and concomitant medication assessment
- Drug administration as outlined in Section 5 and Study Calendar
- Administer MFSI-SF and PROMIS questionnaires

### **7.2.5 After completion of Cycle 2/ 8 weeks ( $\pm 5$ days)**

- CT scans of the chest, abdomen, and pelvis to assess all measurable or non-measurable sites of disease. Regardless of randomization, all subjects will follow up with their physician to discuss results.

## **7.3 End of Treatment: At least 30 days ( $\pm 7$ ) after the last dose of Cycle 2**

- Complete physical examination
- Vital signs including BP, weight and ECOG performance status
- Laboratory testing:
  - Complete Blood Count (CBC) with differential and platelet count??
  - Complete metabolic profile (CMP)
  - PT/INR and aPTT
- Adverse event and concomitant medication assessment
- Administer MFSI-SF and PROMIS questionnaires
- Pill count

## **7.4 Follow-Up ( $\pm 7$ )**

Subjects will be followed every 3 months for 18 months after completion of Cycle 2:

- Disease progression
- Type and start date of additional cancer treatment
- Survival status

## 8 CRITERIA FOR EVALUATION

### 8.1 Definitions Associated with Response Evaluation Criteria in Solid Tumors (RECIST) version 1.1

#### 8.1.1 Measurable disease

The presence of at least one measurable lesion. If the measurable disease is restricted to a solitary lesion, its neoplastic nature should be confirmed by cytology/histology.

#### 8.1.2 Measurable lesions

Measurable lesions are defined as those that can be accurately measured in at least one dimension (longest diameter to be recorded) as  $\geq 20$  mm with chest x-ray, as  $\geq 10$  mm with CT scan, or  $>10$  mm with calipers by clinical exam. All tumor measurements must be recorded in millimeters (or decimal fractions of centimeters).

#### 8.1.3 Non-measurable lesions

All other lesions (or sites of disease), including small lesions (longest diameter  $<10$  mm or pathological lymph nodes with  $\geq 10$  to  $<15$  mm short axis), are considered non-measurable disease. Bone lesions, leptomeningeal disease, ascites, pleural/pericardial effusion, lymphangitis cutis/pulmonis, inflammatory breast disease, cystic lesions, and abdominal masses (not followed by CT or MRI), are considered as non-measurable.

Note: Cystic lesions that meet the criteria for radiographically defined simple cysts should not be considered as malignant lesions (neither measurable nor non-measurable) since they are, by definition, simple cysts.

‘Cystic lesions’ thought to represent cystic metastases can be considered as measurable lesions, if they meet the definition of measurability described above. However, if non-cystic lesions are present in the same subject, these are preferred for selection as target lesions.

#### 8.1.4 Malignant lymph nodes

To be considered pathologically enlarged and measurable, a lymph node must be  $\geq 15$  mm in short axis when assessed by CT scan (CT scan slice thickness recommended to be no greater than 5 mm). At baseline and in follow-up, only the short axis will be measured and followed.

#### 8.1.5 Target lesions

All measurable lesions up to a maximum of 2 lesions per organ and 5 lesions in total, representative of all involved organs, should be identified as target lesions, recorded, and measured at baseline. Target lesions should be selected based on their size (lesions with the longest diameter), be representative of all involved organs, but in addition should be those that lend themselves to reproducible repeated measurements. It may be the case that, on occasion, the largest lesion does not lend itself to reproducible measurement in which circumstance the next largest lesion, which can be measured reproducibly, should be selected. A sum of the diameters (longest for non-nodal lesions, short axis for nodal lesions) for all target lesions will be calculated and reported as the baseline sum diameters. If lymph nodes are to be included in the sum, then only the short axis is added into the sum. The baseline sum diameters will be used as

reference to further characterize any objective tumor regression in the measurable dimension of the disease.

### 8.1.6 Non-target lesions

All other lesions (or sites of disease) including any measurable lesions over and above the 5 target lesions should be identified as non-target lesions and should be recorded at baseline. Measurements of these lesions are not required, but the presence, absence, or in rare cases unequivocal progression of each should be noted throughout follow-up.

### 8.1.7 Response Criteria

#### 8.1.7.1 Evaluation of target lesions

Complete Response (CR)	Disappearance of all target lesions. Any pathological lymph nodes (whether target or non-target) must have reduction in short axis to <10 mm.
Partial Response (PR)	At least a 30% decrease in the sum of the diameters of target lesions, taking as reference the baseline sum diameters
Progressive Disease (PD)	At least a 20% increase in the sum of the diameters of target lesions, taking as reference the smallest sum on study (this includes the baseline sum if that is the smallest on study). In addition to the relative increase of 20%, the sum must also demonstrate an absolute increase of at least 5 mm. (Note: the appearance of one or more new lesions is also considered progressions).
Stable Disease (SD)	Neither sufficient shrinkage to qualify for PR nor sufficient increase to qualify for PD, taking as reference the smallest sum diameters while on study

#### 8.1.7.2 Evaluation of non-target lesions

Complete Response (CR)	Disappearance of all non-target lesions and normalization of tumor marker level. All lymph nodes must be non-pathological in size (<10 mm short axis) Note: If tumor markers are initially above the upper normal limit, they must normalize for a subject to be considered in complete clinical response.
Non-CR/Non-PD	Persistence of one or more non-target lesion(s) and/or maintenance of tumor marker level above the normal limits
Progressive Disease (PD)	Appearance of one or more new lesions and/or unequivocal progression of existing non-target lesions. Unequivocal progression should not normally trump target lesion status. It must be representative of overall disease status change, not a single lesion increase.

Although a clear progression of “non-target” lesions only is exceptional, the opinion of the treating physician should prevail in such circumstances, and the progression status should be confirmed later by the sponsor-investigator.

### 8.1.7.3 Evaluation of best overall response

Target Lesions	Non-Target Lesions	New Lesions	Overall Response
CR	CR	No	CR
CR	Non-CR/Non-PD	No	PR
	Not evaluated	No	PR
PR	Non-CR/Non-PD/not evaluated	No	PR
SD	Non-CR/ Non-PD/not evaluated	No	SD
PD	Any	Yes or No	PD
Any	PD*	Yes or No	PD
Any	Any	Yes	PD

\*In exceptional circumstances, unequivocal progression in non-target lesions may be accepted as disease progression.

Subjects with a global deterioration of health status requiring discontinuation of treatment without objective evidence of disease progression at that time should be classified as having “symptomatic deterioration.” Every effort should be made to document the objective progression even after discontinuation of treatment.

In some circumstances, it may be difficult to distinguish residual disease from normal tissue. When the evaluation of complete response depends on this determination, it is recommended that the residual lesion be investigated (fine needle aspirate/biopsy) to confirm the complete response status.

## 8.2 Definitions for Response Evaluation – RECIST version 1.1

### 8.2.1 First Documentation of Response

The time between initiation of therapy and first documentation of PR or CR.

### 8.2.2 Confirmation of Response

To be assigned a status of complete or partial response, changes in tumor measurements must be confirmed by repeat assessments performed no less than four weeks after the criteria for response are first met.

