**Footnotes:**

CBC=complete blood count; CT=computed tomography; D=days; ECOG=Eastern Cooperative Oncology Group; ICS = informed consent; MFSI-SF= Multidimensional Fatigue Symptom Inventory-Short Form

1. Serum chemistries (creatinine, glucose, total protein, blood urea nitrogen [BUN], total carbon dioxide [CO2], albumin, total bilirubin, alkaline phosphatase, and aspartate transaminase [AST] and alanine transaminase [ALT]) and electrolytes (total calcium, chloride, potassium, sodium)
2. All subjects will have PT/INR/aPTT at screening and End of Treatment Visit. ONLY subjects who are prophylactically treated with an agent such as warfarin or heparin must have close monitoring on Cycle 1 Day 5 and Day 1 of each cycle. If either of these values is above the therapeutic range, subjects should have at least weekly evaluations until INR/PTT is stable based on a measurement that is pre-dose as defined by the local standard of care.
3. Complete only for women of childbearing potential
4. Baseline CTs must be completed within 28 days prior to registration. CTs for re-staging will be performed after Cycle 2 (8 weeks) is complete and may be performed  $\pm$  5 days of scheduled clinic visit. Regardless of randomization, all subjects will follow up with their physician to discuss results.
5. Regorafenib 160 mg PO once daily will be administered for 3 weeks on/1 week off. If subject randomizes to receive Ginseng: 2,000 mg PO per day (1,000 mg BID), every day of each 28-day cycle. For subjects that randomize to ginseng, if regorafenib is held due to toxicity the ginseng may continue per protocol schedule.
6. See Study Procedures Manual for MFSI-SF and PROMIS questionnaires and additional information. The research nurse will provide the questionnaires to the subject as well as instructions on completion of the questionnaires. These instructions should include the importance of the subject completing the surveys without family assistance. The first set of surveys will be administered by the research nurse in the clinic via interview. The remainder of the surveys will be self-administered by the subject in clinic. If the subject has a question regarding the surveys the research nurse or physician will be available to respond. For pill count, please ask the subject to bring their pill bottle to verify number of doses taken at the time of clinic visit.

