7. The End of Treatment visit should occur 30 days after completion of Cycle 2 ( $\pm$  7 days). Subjects who stop treatment prior to completion of Cycle 2 should have the EOT 30 days after discontinuation of treatment. Subjects who have an ongoing  $\geq$  grade 2 or serious AE (SAE) at this visit will continue to be followed until the AE resolves to  $\leq$  Grade 1 or baseline, deemed clinically insignificant, and/or until a new anti-cancer treatment starts, whichever is earlier.
8. Follow up will occur in all subjects after completion of Cycle 2 every 3 months for 18 months. Follow up may be accomplished via clinic visit, phone call, or other avenues as appropriate.
9. Day -7 only ECOG performance status need be obtained.
10. Urinalysis should be done if proteinuria is suspected as per site investigator's discretion.

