### 8.2.5 Objective response rate

The objective response rate is the proportion of all subject with confirmed PR or CR according to RECIST v.1.1, from the start of treatment until disease progression/recurrence (taking as

reference for progressive disease the smallest measurements recorded since the start of treatment).

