Response rate (RR) as an endpoint is defined in section 8.2.5 of the protocol. Objective response (complete response + partial response) rate defined as the proportion of patients who achieve an objective response out of all patients treated on that arm will be estimated along with a 95% confidence interval.

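### Response counts only if confirmed at least four weeks later, but only one post-baseline CT is scheduled (week 8), so scheduled imaging cannot yield a confirmed response

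*Combined protocol and SAP*

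**What the plan says.** **Definition.** Section 8.2.2 makes confirmation a condition of CR or PR status: "changes in tumor measurements must be confirmed by repeat assessments performed no less than four weeks after the criteria for response are first met". Section 8.2.5 carries this into the endpoint: "The objective response rate is the proportion of all subject with confirmed PR or CR according to RECIST v.1.1", assessed "from the start of treatment until disease progression/recurrence". Section 11, under secondary objective 4, adopts it: "Response rate (RR) as an endpoint is defined in section 8.2.5 of the protocol". It then restates the rate without the word confirmed, "defined as the proportion of patients who achieve an objective response out of all patients treated on that arm", and plans an estimate with a 95% confidence interval.

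**Imaging calendar.** After the baseline CT, the Section 7 footnotes give one time point: "CTs for re-staging will be performed after Cycle 2 (8 weeks) is complete", with a 5-day window either side. Sections 5 and 7.2.5 agree. For End of Treatment, "The End of Treatment visit should occur 30 days after completion of Cycle 2", within 7 days either way; neither the calendar column nor Section 7.3 lists a scan there. Section 7.4 follows subjects quarterly for 18 months for progression, new treatment and survival. On how this is done, the footnotes say: "Follow up may be accomplished via clinic visit, phone call, or other avenues as appropriate".

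**Status of the endpoint.** Section 2.2 names response rate as part of secondary objective 4. Section 2.3 does not include it in its endpoint list.

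**The concern.** A confirmed response needs two post-baseline assessments, one that meets the criteria and another at least four weeks later. The calendar supplies one scan. No section schedules a second scan or waives confirmation.

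An analyst who applies Section 8.2.5 to the scheduled scans must report no responses in either arm, even if several subjects had a partial response at week 8. The planned estimate and interval would then say nothing about tumor response. An analyst who also uses unscheduled scans would report a figure that depends partly on who was rescanned and when. Section 5 describes no placebo for the control arm, so rescanning could in principle differ between arms.

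Section 11 leaves out the word confirmed while citing the section that requires it, so a third analyst might report the unconfirmed week-8 rate. The same data could support different published response rates.

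**Working it through.** The documents give no expected response rate and no power for this endpoint, so there is no planned figure to reproduce. The check compares the definition with the calendar and then sizes the consequence.

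**1. Count the assessments.**
- Post-baseline CTs scheduled (Sections 5, 7 and 7.2.5): 1.
- Assessments needed for confirmation (Section 8.2.2): 2, at least 28 days apart.
- Since 1 < 2, no subject can be confirmed on scheduled imaging.

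**2. Place it in time.** This assumes both 28-day cycles run on schedule and the CT window is centred on day 56.
- Week-8 CT: day 56 ± 5 = days 51 to 61.
- Earliest valid confirmation: 51 + 28 = day 79 to 61 + 28 = day 89 (day 84 for a CT on day 56).
- No scan is scheduled on or after those days.

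**3. Result on scheduled imaging at the enrolment targets** (60 and 30, Section 11). The plan names no interval method, so I assume the exact (Clopper-Pearson) one. With zero responders its 95% upper limit is 1 − 0.025^(1/n).
- Ginseng, 0/60: 1 − 0.025^(1/60) = 0.0596, interval 0 to 6.0%.
- No ginseng, 0/30: 1 − 0.025^(1/30) = 0.1157, interval 0 to 11.6%.

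**4. Compare with what the week-8 scans might show.** Responder counts here are assumptions, with no off-schedule confirmation.

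| Assumed week-8 responders | Unconfirmed rate | Confirmed on scheduled imaging |
|---|---|---|
| 0 of 60 | 0% | 0% (upper limit 6.0%) |
| 3 of 60 | 5.0% | 0% (upper limit 6.0%) |
| 4 of 60 | 6.7% | 0% (upper limit 6.0%) |
| 6 of 60 | 10.0% (exact 95% CI 3.8 to 20.5%) | 0% (upper limit 6.0%) |
| 3 of 30 | 10.0% | 0% (upper limit 11.6%) |
| 4 of 30 | 13.3% | 0% (upper limit 11.6%) |

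The two definitions agree only if nobody responds. From four week-8 responders in either arm, the reported interval would exclude the rate seen on the trial's own scans (0.0596 × 60 = 3.6; 0.1157 × 30 = 3.5).

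**5. Non-imaging route.** Section 8.1.2 accepts caliper measurement on clinical examination, and Section 7.3 includes a physical examination at End of Treatment. By footnote 7 that visit falls on day 56 + 30 ± 7 = days 79 to 93. The gap from the CT is then 79 − 61 = 18 to 93 − 51 = 42 days, so 28 days is possible but not assured. Section 7.3 does not ask for tumor measurement.

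**The case against.** The strongest reply is that the definition is not limited to scheduled scans. The Section 8.2.5 window runs to progression, so on a plain reading any scan within it could confirm a response. Later disease assessment is foreseen: Section 7.4 follows progression, Section 8.1.7.3 urges documentation of objective progression after treatment stops, and Sections 8.2.6 and 8.2.7 censor at the last disease evaluation. Section 13.1 provides for entering some standard-of-care data in line with the trial's objectives, and response is one of them. Section 8.2.2 speaks of assessments rather than scans, which leaves the caliper route.

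This stands to the following extent. A reader might infer that the trial must report a zero response rate, or that response can never be confirmed. The documents do not support that: zero is the result on scheduled imaging, and an unscheduled scan or a caliper measurement could confirm a response. A non-zero rate would also not be a pure record of rescanning habits; it would reflect true response and re-assessment frequency together.

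It does not remove the mismatch. None of these sections requires a scan after week 8, fixes its timing or says which unscheduled assessments qualify. Follow-up can be done by telephone. The caliper route serves only superficial lesions.

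A reader might also see a contradiction in the denominators, all subjects in Section 8.2.5 against treated patients in Section 11. Because Section 8.2.5 counts from the start of treatment, the two can be read as the same set. This is a wording matter.

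**Conclusion.** The mismatch is real and follows from the text: confirmation is mandatory, and the calendar provides one post-baseline scan. On scheduled imaging the confirmed response rate is fixed at zero in both arms before any data are seen. Off-schedule assessments can raise it, but their ascertainment is left to local practice. Either way the planned estimate is uninformative or unevenly ascertained.

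The structural conclusion needs no assumption. The limits of 6.0% and 11.6% assume full enrolment, all enrolled subjects in the denominator, an exact interval and no off-schedule confirmation. The four-responder threshold adds assumed responder counts.

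The reach is limited. Response is estimated only, with no planned between-arm test. A reader might infer that the trial's main conclusions are weakened; the documents do not support that, since the fatigue primary, the sample size and overall survival do not use response. The plan should nevertheless be corrected, because a named objective should not rest on a definition that its own calendar cannot meet.

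**What to change.** Use one definition in Sections 8.2.2, 8.2.5 and 11: CR or PR at the week-8 re-staging CT, labelled unconfirmed. Specifically:
- use one denominator in both places, all treated subjects, with a missing week-8 scan counted as non-response;
- drop the run-to-progression window in Section 8.2.5 for this endpoint, since it does not fit a single assessment;
- name the confidence interval method;
- report any later confirmation from standard-of-care scans descriptively only.

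No scan is added. The cost is an amendment, which under Section 13.4 needs IRB and drug-supplier approval. An unconfirmed rate is more optimistic than a confirmed one, by an amount the documents do not give. Section 3.1 asks only for radiographically assessable disease, so the denominator may include subjects without measurable lesions; the report should say how many.

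If the sponsor keeps confirmation, the response definition and the imaging calendar must be reconciled, and the plan must say which assessments count.

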### 8.2.3 Duration of Response

Duration of overall response—the period measured from the time that measurement criteria are met for complete or partial response (whichever status is recorded first) until the date that recurrent or progressive disease is objectively documented (taking as reference for progressive disease the smallest measurements recorded since treatment started).

### 8.2.4 Duration of Overall Complete Response

The period measured from the time that measurement criteria are met for complete response until the first date that recurrent disease is objectively documented.

